MRI Quality Control: The quality control of the scanner is done by Sheba Department of Radiology in conjunction with GE field engineers. This is augmented by administration of a MAGPHAN Quantitative Imaging phantom which has been consistently scanned at least monthly since April 2009; the scanner has been highly stable over time. Based on our experience, we anticipate technical problems <2%. There is sufficient time in the session for rescanning if motion or other artifacts are observed. Trained and certified MR technologists operate the console; scans are prescribed in a standardized fashion and assessed at the scanner for acceptable quality. Scans are downloaded to the imaging lab server immediately after the session and the post-processing procedures are implemented including an additional quality check by the study team. If baseline re-imaging is necessary, study intervention will be delayed until satisfactory images are obtained.

MRI Data Backup: Multiple backups are performed to prevent technical loss of data. At the scan console, the exam is backed up to DVD and kept at the MR facility. The exam is also uploaded to a PACs server and permanently archived. A complete copy is downloaded to a 40TB RAID6 server and weekly backups (to a separately located server) are made of processed and incremental data.

MRI Image Processing: Images will be pre-processed prior to statistical analysis using well established tools and pipelines including SPM12 and FSL. The pipelines are scripted and extendable such that improved methods developed in the software or locally can easily be applied to all data in batch. The pipeline steps include: 1) Conversion of images to NIFTI file format for broad compatibility between software packages; 2) Insertion of the

exam into the imaging SQL database (so Drs. [name], [name], and [name] can view the data online via web tools); 3) coregistration of each ASL CBF map to the baseline map which is in turn coregistered to the T1-weighted 3D SPGR volume at baseline; coregistration uses a mutual information algorithm and linear least squares minimization in SPM12; 4) transformation into MNI canonical atlas space using the ICBM 152 template in SPM12. Finally, data are smoothed with a Gaussian kernel of 8mm FWHM to accommodate individual variability and comply with assumptions of random field theory necessary for statistical analysis of the images.

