T2FLAIR images will be segmented according to methods previously used by our group¹⁰⁶. WMH will be used as covariates in the second-level analysis.

FDG-PET: [name] [name], Chair of the Nuclear Medicine Department at Sheba, will oversee acquisition of [F18]FDG on a Philips Gemini GXL + PET scanner in 3D mode.

[F18]FDG-PET Acquisition: Participants will be studied after a minimum 4 hour fast (water allowed). Because participants with glucoregulatory dysfunction are being imaged, blood glucose will be closely monitored prior to the injection of [F18]FDG. Blood glucose prior to [F18]FDG administration must be ≤ 180 mg/dL for [F18]FDG to be injected. Following injection with 5.0 ± 0.5 mCi of [18F][F18]FDG participants will remain awake but relaxed in a quiet room. Imaging will begin 45 min. post injection, and the scan acquired as six 5-min. frames. A 5-min. transmission scan will be acquired following the emission scan. The dynamic PET data will be reconstructed using ECAT v7.2.2 software. A filtered back projection algorithm (DIFT) will be used with brain mode sinogram trimming, zoom = 2.8, and a 4mm Gaussian filter to a reconstructed image of 128 x 128 x 63 voxel matrix (voxel size = 1.84mm x 1.84mm x 2.43mm). The PET data will be corrected for the attenuation of annihilation radiation (using segmented attenuation maps), scanner normalization, and scatter radiation.

[F18]FDG image processing: Data will be transferred to the ADRC imaging lab at the UW-Madison using a secure protocol our group has in place. The reconstructed images will be used for comparison of regional differences of [F18]FDG uptake in the targeted areas of the brain. The dynamic [F18]FDG will first be corrected for frame to frame motion using SPM12 software. Any frames with excessive motion will be discarded from further processing. The data will then be summed to create a single image representing [F18]FDG uptake in the brain from the period of 45–75 minutes.

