This image will then be scaled so the mean whole brain activity will be equal for all subject scans. *Images will be corrected for atrophy based on the three-compartment approach (includes GM, WM and CSF) based on the method published by Meltzer et al.^{107, 108}. In brief, the MR T1 image is segmented in SPM12 to provide GM, WM & CSF maps. The partial volume corrected gray matter tissue tracer concentration will be used for the second level group analysis, extracted from regions of interest (dorsolateral prefrontal, medial temporal, and lateral parietal cortices).* These regions have been selected based on their vulnerability to T2D and AD. Data will be extracted bilaterally using the Automated Anatomical Labeling (AAL) atlas implemented in WFU PickAtlas, and averaged across hemispheres prior to being entered into statistical models. Secondary analyses will include exploratory whole-brain analyses conducted on a voxel-wise basis.

D2K. Inflammatory and diabetes and dementia related markers - Morning bloods will be obtained after a 10-hour fast, then centrifuged. Bloods will be stored at -70C until determination in Sheba Medical center.

We will analyze the bloods to determine the diabetes and dementia related biomarkers in several well established methods, like:

High sensitivity C-reactive protein- CRP levels will be measured with a sandwich-type ELISA in which polyclonal rabbit anti-CRP antibodies are used as catching antibodies and a biotinylated mAb against CRP (CLB anti-CRP-2) is used as the detecting antibody. The inter- and intra-assay coefficients of variation are expected to be less than 5%.

Interleukin-6- IL-6 will be measured using a commercial solid phase immulite (Diagnostic Products Corporation [DPC], Los Angeles, CA, USA). Reported inter-assay coefficient of variation is 6% and intra-assay 4%, with a detection limit of 1.0 pg/ml.

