Aim 1. Power is presented for detecting the difference in mean change (from baseline to 12 weeks) in overall cognition z-scores between the sham and HBOT treatment groups. Power calculations are based on two-sample t-tests and are conducted with a 2-sided 5% significance level (**Table 3**). A 2-sample t-test provides a more conservative power estimate than the proposed mixed model approach, which is expected to explain more variability and thus have more power to detect the same effect size with the same sample size.

The predicted mean change in the sham group from baseline to 12 weeks is -0.02 (based on the IDCD 12-week change in overall cognition). Assuming an SD of 0.50 in both the sham and HBOT groups, with a minimum sample size of 67 patients per arm, we have 80% power to detect an improvement in the HBOT group of 0.224, a “medium” effect size of 0.49. To account for an anticipated dropout rate of 13% (a reasonable estimate compared to the 5% dropout rate in our stroke study), we plan to enroll 77 patients per group for a total of 154 patients. Our HBOT trial years after mild traumatic brain injury⁷⁴ had an effect size of 0.47 for information speed processing which is clinically comparable to our primary outcome measure of overall cognition, and our HBOT trial on stroke patients⁷⁸ showed an effect size of 0.49 for the National Institutes of Health stroke scale, suggesting our detectable effect size of 0.49 is feasible.

Aim 2: As for Aim 1, power is presented for detecting the difference in the mean changes in CBF velocity and cerebral glucose utilization between the Sham and HBOT groups. Assuming a mean change in CBF velocity of -0.45 in the Sham group and an SD of 5.6 in both groups, with a minimum sample size of 67 patients per arm we have 80% power to detect an improvement in the HBOT group of 2.28, an effect size of 0.49. *To account for an anticipated dropout rate of 13%, we plan to enroll 77 patients per group for a total of 154 patients.* For cerebral glucose utilization, assuming a mean change in the sham group of -0.08 and an SD of 4.40 in both groups, with

Table 3: Two group t-test of equal means, equal n's)*			
	Outcome		
	Overall Cognition z-score	CBFV [†]	CGU [‡]
Sham Mean Change, D ₁	-0.020	-0.450	-0.08
HBOT Mean Change, D ₂	0.224	2.28	2.065
Difference in means, D ₁ -D ₂	-0.244	-2.73	-2.145
HBOT SD	0.50	5.60	4.40
Minimum N per group	67	67	67
Enrollment N per group**	77	77	77

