* Test of significance level=0.05; **assuming a 13% drop-out rate; Two-sided test; Power=80%; Effect size=0.49; [†] CBF=CBF; [‡]CGU = cerebral glucose utilization

67 patients per group we are powered to detect an improvement in the HBOT group of 2.065, an effect size of 0.49. According to literature sources^{48, 123} these are observable effect sizes.

D8. Future directions: *If this pilot study is successful, we will pursue a multi-center large-scale clinical trial to provide definitive evidence for the benefits of HBOT to cognition in T2D patients at high risk for dementia, taking advantage of the new knowledge acquired in this pilot study regarding effect sizes, design, recruitment strategies, attrition, cognitive outcomes, biomarkers, and subgroups benefitting most. Since HBOT is widely available and well tolerated, the proposed trial's success may suggest testing HBOT efficacy in non-T2D elderly with MCI as well.*

E. HUMAN SUBJECTS RESEARCH

1. Risks to the Subjects - Human Subject Involvement and Characteristics.

a. Involvement and Characteristics:

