HBOT- Hyperbaric oxygen therapy is generally safe and well tolerated. Most side effects are mild and reversible, although severe consequences can occur in rare cases⁸⁹. Middle ear barotrauma is the most common side effect of hyperbaric oxygen, with an incidence of less than 2%⁸⁹. Middle ear effusions (which may be hemorrhagic) and tympanic membrane rupture occur in less than 1% of patients. Middle ear symptoms may be alleviated by teaching the patient autoinflation techniques which will be done before subjects enter the chamber. Sinus barotrauma (sinus squeeze) is the second most common complication of hyperbaric oxygen and is usually seen in patients with upper respiratory tract infections. Subjects with such conditions will not be allowed to continue the intervention until symptoms are over. Seizures due to central nervous system oxygen toxicity are a rare but a possible dramatic consequence of HBOT; estimates of incidence range from 1 in about 3000 to 2.4 per 100,000 treatments^{90, 91}. The risk is increased by HBOT exposure greater than 120 minutes and by pressures greater than 2.8 ATA. In our study, patients will be treated for 90 minutes and at 2.0 ATA. Patients receiving glucocorticoids, insulin, thyroid replacement, and sympathomimetic medications may be at higher risk of central

nervous system oxygen toxicity. HBOT has been associated with hypoglycemia in some patients with diabetes, and hypoglycemia should therefore be considered in the differential diagnosis of HBOT-associated seizures⁹². Seizures due to oxygen toxicity do not typically result in permanent structural brain damage⁸⁹. In the unlikely case of a seizure in this trial, it will be managed acutely by reducing the inspired oxygen concentration to that of air (FIO₂ = 0.21), administering anticonvulsant therapy, and terminating hyperbaric treatment. Importantly, a nurse from the Hyperbaric Unit team will be at all times with the subjects inside the chamber, and a physician will be at all times in the Unit providing immediate medical response if any of the adverse events arises. All other potential adverse effects (reversible myopia, pulmonary oxygen toxicity) are very rare and reversible.

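### The 80% power stated for FDG-PET assumes no scan is lost beyond 13% dropout, although FDG is withheld above 180 mg/dL in a sample where everyone has diabetes

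*Combined protocol and SAP*

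**What the plan says.** Section D2h names CBF and FDG-PET as the primary imaging outcomes. For FDG, D2j ([F18]FDG-PET Acquisition) sets a glucose limit: "Blood glucose prior to [F18]FDG administration must be ≤ 180 mg/dL for [F18]FDG to be injected". It gives no expected refusal rate and does not say what happens to a refused scan. The processing steps add a dependence on MRI, because the atrophy correction uses a segmented T1 image: "In brief, the MR T1 image is segmented in SPM12 to provide GM, WM & CSF maps".

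For power, D7 states: "Power calculations are based on two-sample t-tests and are conducted with a 2-sided 5% significance level". For CBF it claims that "with a minimum sample size of 67 patients per arm we have 80% power to detect an improvement in the HBOT group of 2.28", and for CGU that with "67 patients per group we are powered to detect an improvement in the HBOT group of 2.065". Table 3 carries 67 minimum and 77 enrolled per arm for cognition, CBF and CGU alike. The one allowance is 13% dropout, justified in D7 by comparison with subject dropout in the team's stroke trial.

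Scan loss is discussed only under MRI Quality Control in D2j: "Based on our experience, we anticipate technical problems <2" per cent. That paragraph allows rescanning within the session and delays the intervention if baseline imaging must be repeated.

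D6 excludes patients who lack a baseline value of a continuous efficacy outcome and uses maximum likelihood for unobserved follow-up visits. HbA1c is one of several covariates that enter a model only on baseline imbalance (p<0.1) or association with the response (p<0.15).

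**The concern.** A change in CGU needs more than a patient who stays in the trial. It needs a PET scan before treatment and another at 12 weeks, each with pre-injection glucose at or below the limit, and a usable T1 image. Cognition has no such condition. Giving both outcomes the same evaluable number treats every retained patient as having two usable PET scans.

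Two things are at stake. The first is the power quoted for a primary imaging outcome, which also feeds the mediation analysis. The second is how missing scans are handled. A scan refused for high glucose is missing for a reason tied to glycaemia. Maximum likelihood deals with that properly only to the extent that the model contains variables explaining the missingness. Under D6, HbA1c may or may not be in the FDG model, depending on a significance test.

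**Working it through.** **Inputs.** From D7 and Table 3: CGU sham change -0.08, HBOT change 2.065, SD 4.40; two-sided 5% two-sample t-test; 67 evaluable and 77 enrolled per arm; 13% dropout. For CBF: "Assuming a mean change in CBF velocity of -0.45 in the Sham group and an SD of 5.6 in both groups", with an HBOT change of 2.28. From D2j: MRI technical problems below 2%. The FDG loss rate is not in the documents and is assumed below.

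**Reproducing the plan.**
- CGU: d = (2.065 + 0.08)/4.40 = 2.145/4.40 = 0.4875.
- CBF: d = (2.28 + 0.45)/5.60 = 2.73/5.60 = 0.4875.
- Noncentral t power at 67 per arm: 79.98% for both. The stated 80% reproduces.
- Dropout: 77 x 0.87 = 66.99. (67/0.87 = 77.01, so strict rounding up gives 78; the difference is immaterial.) The allowance is used up by subject dropout alone.

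**Adding FDG scan loss.** Let L be the proportion of scans permanently lost at each of the two visits, independently and for any reason, with both scans needed. Evaluable n per arm = 67 x (1 - L)². Enrolment that restores 67 evaluable = 67/[0.87 x (1 - L)²], rounded up.

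| L per scan (assumed) | Evaluable per arm | t-test power | Enrolment per arm to restore 67 |
|---|---|---|---|
| 0 | 67 | 80.0% | 78 |
| 2% | 64.3 | 78.4% | 81 |
| 5% | 60.5 | 75.8% | 86 |
| 10% | 54.3 | 71.1% | 96 |

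If L is instead the total extra loss over both visits, n = 67 x (1 - L), and power at 2%, 5% and 10% is 79.2%, 77.9% and 75.7%.

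**CBF for comparison.** The glucose limit does not apply to ASL. Taking the plan's below-2% bound as exactly 2%, power is 79.2% if it applies once and 78.4% if it applies to both scans with no rescan. The rescan provisions make the loss smaller still.

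**What baseline adjustment could recover.** Read SD 4.40 as the SD of change and let r be the correlation between baseline and 12 weeks. Adjusting for baseline multiplies the variance by (1 + r)/2, so the effective d is 0.4875/√[(1 + r)/2]. The documents give no r.

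| L per scan | r = 0.5 | r = 0.7 | r = 0.9 |
|---|---|---|---|
| 2% | 88.7% | 84.5% | 80.4% |
| 5% | 86.7% | 82.2% | 77.9% |
| 10% | 82.8% | 77.9% | 73.3% |

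These figures ignore the random effect for treatment cluster in D6. That effect is not in the power calculation, and any within-cluster correlation would lower them.

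**Enrolment.** D2a says 250 will be enrolled; D7 and section E say 154. At 125 per arm and 13% dropout, 108.75 remain. With 20% total extra FDG loss that is 87.0 per arm and 89.2% power; with 30% it is 84.8%.

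**The case against.** The strongest reply is that no shortfall has been shown. The documents give no refusal rate, and a refused injection need not be a lost scan: the PET is on its own day and could be rebooked. D7 describes the t-test as conservative relative to the mixed model, and the second table shows that adjustment could absorb the loss. Dropout itself is uncertain: D2g reports 5% to 20% in the team's own trials, which at 77 enrolled means 73.2 to 61.6 completers and 83% to 77% power before any scan is lost. If 250 were enrolled, the question would largely disappear. And the trial describes itself as a pilot.

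Most of this stands, and it rules out any firm statement that FDG power falls short. It does not supply the missing assumption. The gain from the mixed model is not quantified, and the cluster effect works against it. Rebooking is possible but is written only for MRI, while a baseline PET that is never obtained removes the patient under D6.

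Two stronger readings are tempting. A reader might infer that the imaging power as a whole, CBF included, is not achieved. The plan's own MRI figure and its rescan and re-imaging provisions do not support that. A reader might also infer that treatment will make scan loss unequal between arms, because section E notes that "HBOT has been associated with hypoglycemia in some patients with diabetes". That sentence concerns the differential diagnosis of seizures during treatment. It does not say that fasting glucose is lower at a later PET visit, and the baseline scan precedes treatment.

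**Conclusion.** The point holds for FDG and is moderate in size. The stated 80% is correct arithmetic for 67 evaluable patients per arm, but it rests on the unstated assumption that no PET scan is lost beyond 13% dropout. Under assumed losses of 2%, 5% or 10% at each of two scans, t-test power is about 78%, 76% or 71%. Whether the planned analysis would fall below 80% depends on the baseline correlation, the cluster effect, actual dropout, how many refused scans are recovered, and which enrolment figure applies. None of these is settled by the documents. For CBF, power of 78% to 79% at the plan's own bound is no material departure from 80%. Unequal scan loss by arm remains a possibility and is not demonstrated.

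**What to change.** 1. **D2a, D7 and section E:** reconcile enrolment of 250 with 154, since the FDG conclusion depends on it.
2. **D7 and Table 3:** give CGU its own evaluable number and state FDG power over a range of scan loss, labelled as an assumption. The first table above would serve if 154 is confirmed.
3. **D2j, FDG-PET Acquisition:** state that a scan refused for glucose may be rebooked, and for baseline scans that this happens before the intervention starts, in line with the existing MRI provision. The glucose limit itself is not in question here.
4. **D6:** prespecify baseline HbA1c as a fixed covariate in the FDG model in place of entry by the p<0.1 or p<0.15 rule. It is already among the planned blood markers. It captures glycaemia at the 12-week scan only in part, so it reduces the dependence of missingness on unmodelled glycaemia without removing it.

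The cost is some wording, an occasional rebooked scan slot and one degree of freedom in the FDG model. The stated FDG power becomes slightly less favourable.

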D2c. Procedures- **Table 2** presents study procedures for each subject. HBOT sessions will take place in Asaf Harofeh Medical Center; informed consent and all other assessments, including cognitive, functional, MRI, and FDG-PET will be performed at the Sheba Medical Center. Adverse event monitoring is done at every HBOT and sham session, by a nurse in the chamber throughout the session and a physician always present. Physical exams and blood collection for safety monitoring will occur before randomization, and at 12 weeks. Medication review will occur before randomization, before and after the intervention, and 6 and 12 months later, with cognitive testing at these times except before randomization. The T2D-related biomarkers (Blood test, MRI ASL and FDG-PET) will be assessed before and after the intervention, and 12 months later. After intervention, a questionnaire will examine whether blindness was maintained. At the end of the participant's 12 months' participation in the trial, the participant can choose to receive HBOT treatment for which the costs will be covered by the study team. At the end of the second HBOT treatment course, an additional neuropsychological assessment will be administered to the participants.

D2d. Randomization and Blinding of Intervention-Eligible candidates will be randomized with equal probability to the HBOT and sham interventions. When a cluster of at least 3 subjects from one of the interventions is filled, the intervention for that cluster will begin (77 subjects will be recruited for each treatment). Clusters will be a random effect in the analyses (see D6). Three study technicians who activate HBOT or sham protocol sessions will be the only unblinded staff who have the key for the subjects' group assignments. All subjects and other clinic staff will remain blinded to group assignment. Study nurses will monitor AEs during all sessions and a physician will be present during each session. Importantly, staff from Sheba, who assesses outcomes, will not be exposed to the subjects during their intervention and vice-versa.

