D6. Statistical Analysis Plan- Efficacy analyses will be performed for the intent-to-treat (ITT) population, our primary analysis, and for fully and partially compliant per-protocol (PP) populations. The ITT population will include all participants in the group to which they were randomized, regardless of any protocol deviation including non-compliance, adverse events, or loss of follow-up. The PP populations will include participants in the group according to the intervention actually received, but a separate analysis will be performed for those who were fully compliant (at least 80% of sessions completed) and for those who were partially compliant (at least one session completed). A complier-average causal effect (CACE) analysis using a latent class modeling approach will also be performed on both fully and partially compliant populations. Patients missing a baseline value of a continuous efficacy outcome measure will be excluded from all analyses and maximum likelihood estimation methods will be used to handle missing data arising from an unobserved follow-up visit¹²².

Aims 1a and 1b: The primary (overall cognition) and secondary (executive functions, episodic memory domains, and computer-based tests) cognitive outcome measures (all summaries of z-scores), will each be analyzed using a mixed model analysis of covariance (ANCOVA) with time of assessment (baseline or 12 weeks) as the within-subjects factor, treatment group (HBOT vs. sham) as the between-subjects factor and baseline value of the outcome measure as the covariate. *Both, subject and 'cluster' (the variable used to identify to which group of at least 3 subjects each individual is assigned) will be modeled as random effects to account for the correlation among repeated measurements made over time within a subject as well as potential 'cluster effects' arising from blocks of at least 3 patients receiving treatment at a particular time after randomization.* An interaction term between time of assessment and treatment group will be included in each model allowing for estimation of the mean change from baseline to 12 weeks in each treatment group as well as a test for difference

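### D6 promises an ITT analysis of all randomised participants, then excludes from all analyses anyone missing a baseline value; the rule should be per outcome and keep these participants

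*Combined protocol and SAP*

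**What the plan says.** Section D6 sets the primary population: "Efficacy analyses will be performed for the intent-to-treat (ITT) population, our primary analysis". It defines that population without exception: "The ITT population will include all participants in the group to which they were randomized, regardless of any protocol deviation". Later in the same paragraph it adds: "Patients missing a baseline value of a continuous efficacy outcome measure will be excluded from all analyses". Likelihood methods are reserved for the other kind of gap: "maximum likelihood estimation methods will be used to handle missing data arising from an unobserved follow-up visit".

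In the model for the cognitive outcomes, baseline appears twice. It is a level of the repeated factor, "time of assessment (baseline or 12 weeks) as the within-subjects factor", and it is also on the right-hand side, "baseline value of the outcome measure as the covariate".

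On timing, D2c lists the medication reviews (before randomisation, before and after the intervention, and at 6 and 12 months) and continues "with cognitive testing at these times except before randomization". Table 2 places group assignment, baseline cognition, MRI and FDG-PET in one Baseline column.

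On imaging, the FDG-PET acquisition text in D2j says "Blood glucose prior to [F18]FDG administration must be" at or below 180 mg/dL. The undertaking to hold back the intervention until baseline images are usable stands under MRI quality control only.

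**The concern.** A participant who is randomised but has no baseline value belongs to the ITT set under one sentence and is removed under another. D6 gives no modified-ITT label, no imputation of a missing baseline, and no sensitivity analysis that restores these participants. Any cognitive results they have at 12 weeks, 6 months and 12 months go unused.

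The scope of the rule is also unclear. It is triggered by one continuous outcome and applies to all analyses. Taken at its word, a participant with complete cognitive data leaves the primary analysis because one scan was not obtained. There are foreseeable ways to lack a baseline value. Every participant has type 2 diabetes, and the PET tracer is withheld above a glucose limit. The primary composite sums eight test scores, and neither D2h nor D6 says what happens if one of them is missing.

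At stake are whether the primary analysis can be called ITT as the plan defines it, and some precision.

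**Working it through.** **1. The two rules side by side.** The ITT definition covers all participants as randomised. The examples of deviations it tolerates (non-compliance, adverse events, loss of follow-up) do not name a missing baseline, so the conflict rests on the word covering all participants. The exclusion rule has no exception for the ITT set. The conflict is therefore explicit, whatever the number affected.

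**2. Can a randomised participant lack a baseline?** The evidence on order is mixed.
- D2c separates a time before randomisation from a time before the intervention, and places cognitive testing at the second but not the first. This leans towards baseline cognition following randomisation.
- Table 2 puts assignment and baseline testing in the same column and gives no order within it.
- D2c puts safety blood collection before randomisation, while Table 2 marks blood tests at Baseline and not at Screen. Some Baseline procedures may therefore come first.
- In D2d, willingness to accept either arm is confirmed before the baseline visit, which fits a later assignment.

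The order is not settled. Even if baseline testing comes first, anyone randomised without a usable value still falls under both rules.

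**3. The plan's own sample size (D7, Table 3).** Inputs: sham change −0.02, HBOT change 0.224, SD 0.50, two-sided 5%, power 80%, 13% dropout.
- Difference = 0.224 − (−0.02) = 0.244; standardised, 0.244 / 0.50 = 0.488.
- The two-sample t-test needs 66.9 per arm, so 67. Power at 67 is 80.1%. The plan's figure reproduces.
- 67 / 0.87 = 77.01. Strict rounding up gives 78; the stated 77 is within rounding, since 77 × 0.87 = 66.99.

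Dropout uses the whole allowance, so any further exclusion takes the analysed set below 67.

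**4. Effect of the exclusion rule.** The documents give no rate of missing baselines, so the share m is an assumption. Evaluable n per arm = 66.99 × (1 − m).

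| Assumed m | n per arm | t-test power |
|---|---|---|
| 0% | 67.0 | 80.1% |
| 2% | 65.7 | 79.3% |
| 5% | 63.6 | 78.0% |
| 10% | 60.3 | 75.7% |

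**5. How much can be recovered?** If only an imaging baseline is missing, a per-outcome rule recovers the whole loss for the cognitive analysis. If the cognitive baseline is missing, a participant with follow-up only carries a fraction 1 − ρ² of the information of a complete one, where ρ is the baseline to follow-up correlation (assumed; not in the documents). Effective n = 66.99 × [(1 − m) + m(1 − ρ²)].
- m = 5%: ρ = 0.5 gives 66.2 and 79.6%; ρ = 0.9 gives 64.3 and 78.4%. Exclusion gives 78.0%.
- m = 10%: ρ = 0.5 gives 65.3 and 79.0%; ρ = 0.9 gives 61.6 and 76.6%. Exclusion gives 75.7%.

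**6. Allowing for baseline adjustment.** With the SD of change fixed at 0.50, adjusting for baseline multiplies the variance by (1 + ρ)/2, so the standardised effect becomes 0.488 / √[(1 + ρ)/2]. Ignoring clustering, at m = 10% (n = 60.3):
- ρ = 0.5: effect 0.563, power 86.6%
- ρ = 0.7: effect 0.529, power 82.2%
- ρ = 0.8: effect 0.514, power 80.0%
- ρ = 0.9: effect 0.501, power 77.8%

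**The case against.** The natural reading may be narrower. D6 goes on to analyse each outcome separately with its own baseline as covariate, and the phrase about all analyses follows directly on the ITT, per-protocol and CACE analyses. It can be read as all of those for the outcome concerned. This stands as a plausible intention, but the text does not state it.

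The ANCOVA needs its covariate, so a participant without the cognitive baseline would leave that model in any case. This stands in part. It applies only to the outcome that lacks a baseline, and only if baseline is neither imputed nor modelled as a response. It does mean that the power loss is not wholly avoidable.

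The size is assumed. D2j does not say that a PET session stopped for high glucose is abandoned rather than rebooked. The nearest stated rate is under 2% for MRI technical problems. Some early withdrawals may overlap with missing baselines, and D7 itself calls the t-test conservative. All of this stands.

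A reader might infer two stronger points. The first is that D2c proves the exclusion happens after randomisation; it leans that way, but Table 2 leaves the order open. The second is that the primary result is biased, because participants with high glucose are removed selectively. Poorer glycaemic control among them is an inference. Baseline is taken before treatment, and participants and outcome assessors are blinded, so missingness has no evident route to depend on arm. The documents do not support a claim of bias between arms.

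**Conclusion.** The concern holds as an internal contradiction with a modest cost. D6 states an ITT set of all randomised participants and, in the same paragraph, a rule that removes some of them and discards their observed follow-up. That is an undeclared departure from ITT. Whether a missing baseline on one outcome removes a participant from the analysis of another is ambiguous; the literal text says that it does.

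On the plan's own t-test basis the loss is about 1, 2 or 4 percentage points of power at an assumed 2%, 5% or 10% excluded. Those figures rest on an assumed rate, on exclusions being additional to the full 13% dropout, and on no gain from baseline adjustment. Adjustment could keep power at or above 80% for correlations up to about 0.8, even at 10% excluded, if clustering is ignored. The stated sample size is not in error.

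**What to change.** Replace the exclusion sentence in D6 with:

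> A missing baseline on one outcome affects only the analysis of that outcome. All randomised participants with at least one observed value of the outcome, at baseline or follow-up, are kept in its ITT analysis.

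The words covering baseline or follow-up matter. A rule requiring a post-baseline value would drop participants with baseline only, whom the present plan keeps because baseline is a level of the repeated factor and maximum likelihood covers absent follow-up.

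Implement it in one of two ways:
- a likelihood model with baseline and follow-up both as responses and a common baseline mean across arms; or
- if baseline stays a covariate, fill a missing baseline with the mean pooled over arms, without using treatment assignment.

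Report the analysis restricted to participants with an observed baseline as a sensitivity analysis.

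The cost is SAP wording, standard software options and slightly more analysis work. No new data are needed.
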